3.3 Study Population

For entry into the study, the following criteria MUST be met:

3.3.1 Inclusion Criteria

1) Signed Written Informed Consent

- a) Subjects must have signed and dated an IRB/IEC-approved written informed consent form in accordance with regulatory and institutional guidelines. This must be obtained before the performance of any protocol-related procedures that are not part of normal subject care.
- b) Subjects must be willing and able to comply with scheduled visits, treatment schedule, laboratory tests, and other requirements of the study.

2. Target Population

- a) ECOG PS:
 - i) PS 0 to 1 (Subgroup 1)
 - ii) PS 2 (Subgroup 2; minimum of 95 enrolled (81 treated) subjects. The Scientific Steering Committee will provide guidance and scientific expertise on the risk/benefit ratio following a Safety Management Plan).
- b) Subjects with histologically or cytologically-documented SqNSCLC who presented with stage IIIb/stage IV disease or who developed recurrent or progressive disease following prior definitive therapy for localized or local advanced disease. NOTE: A fresh biopsy is not required to take part in the study.
- c) Subjects must have experienced disease recurrence or progression during or after one prior platinum doublet-based chemotherapy regimen for advanced or metastatic disease.
 - i) Maintenance therapy following platinum doublet-based chemotherapy is not considered as a separate regimen of therapy
 - ii) Subjects who received platinum-containing adjuvant, neoadjuvant or definitive chemoradiation therapy given for locally advanced disease, and developed recurrent (local or metastatic) disease within 6 months of completing therapy are eligible.
 - iii) Subjects with recurrent disease > 6 months after platinum-containing adjuvant, neoadjuvant or definitive chemoradiation therapy given for locally advanced disease, who also subsequently progressed during or after a platinum doublet-based regimen given to treat the recurrence, are eligible.
- d) Subjects must have evaluable disease by CT or MRI per RECIST 1.1 criteria (radiographic tumor assessment performed within 28 days of first dose of study drug) or clinically apparent disease that the investigator can follow for response.
- e) Subjects with CNS metastases:
 - i) Subjects are eligible if CNS metastases are treated and subjects have neurologically returned to baseline (except for residual signs or symptoms related to the CNS treatment) for at least 2 weeks prior to first dose. In addition, subjects must be either off corticosteroids or on a stable or decreasing dose ≤ 10 mg daily prednisone (or equivalent)
OR
 - ii) Subjects are eligible if they have previously untreated CNS metastases that are neurologically asymptomatic. In addition, subjects must be either off corticosteroids or on a stable or decreasing dose of ≤ 10 mg daily prednisone (or equivalent).
- f) As of Amendment 01, this criterion is no longer applicable.
- g) Prior palliative radiotherapy must have been completed at least 14 days prior to study drug administration. See [Section 3.4.3.1](#) for guidance on palliative radiotherapy during study treatment.
- h) As of Amendment 01, this criterion is no longer applicable.
- i) As of Amendment 01, this criterion is no longer applicable.

- j) Screening laboratory values must meet the following criteria prior to commencement of treatment:
 - i) WBCs $\geq 2000/\mu\text{L}$
 - ii) Neutrophils $\geq 1500/\mu\text{L}$
 - iii) Platelets $\geq 100 \times 10^3/\mu\text{L}$
 - iv) Hemoglobin $\geq 9.0 \text{ g/dL}$
 - v) Serum creatinine of $\leq 1.5 \times \text{ULN}$ or creatinine clearance (CrCl) $> 40 \text{ mL/minute}$ (using Cockcroft/Gault formula)
 - (1) Female CrCl= $[(140 - \text{age in years}) \times \text{weight in kg} \times 0.85] \div (72 \times \text{serum creatinine in mg/ dL})$
 - (2) Male CrCl= $[(140 - \text{age in years}) \times \text{weight in kg} \times 1.00] \div (72 \times \text{serum creatinine in mg/ dL})$
 - vi) AST $\leq 3 \times \text{ULN}$
 - vii) ALT $\leq 3 \times \text{ULN}$
 - viii) Total bilirubin $\leq 1.5 \times \text{ULN}$ (except subjects with Gilbert Syndrome, who must have total bilirubin $< 3.0 \text{ mg/dL}$)
- k) As of Amendment 01, this criterion is no longer applicable.
- l) Subject Re-enrollment: This study permits the re-enrollment of a subject who has discontinued the study as a pre-treatment failure (ie, subject has not been randomized / has not been treated). If re-enrolled, the subject must be re-consented.
- m) Prior lines of antineoplastic therapy, including chemotherapy, hormonal therapy, immunotherapy, surgical resection of lesions, non-palliative radiation therapy, or standard or investigational agents for treatment of NSCLC, must be completed 28 days prior to the first dose of nivolumab

3. Age and Reproductive Status

- a) Males and Females, ages 18 or older
- b) Women of childbearing potential (WOCBP) must have a negative serum or urine pregnancy test (minimum sensitivity 25 IU/L or equivalent units of HCG) within 24 hours prior to the start of study drug
- c) Women must not be breastfeeding
- d) WOCBP must agree to follow instructions for method(s) of contraception for the duration of treatment with nivolumab plus approximately 5 half-lives of nivolumab plus 30 days (duration of ovulatory cycle) for a total of 5 months post-treatment completion.
- e) Males who are sexually active with WOCBP must agree to follow instructions for method(s) of contraception for the duration of treatment with nivolumab plus approximately 5 half-lives of the study drug plus 90 days (duration of sperm turnover) for a total of 7 months post-treatment completion.
- f) Azoospermic males and WOCBP who are continuously not heterosexually active are exempt from contraceptive requirements. However, they must still undergo pregnancy testing as described in this section.

Investigators shall counsel WOCBP and male subjects who are sexually active with WOCBP on the importance of pregnancy prevention and the implications of an unexpected pregnancy. Investigators shall advise WOCBP and male subjects who are sexually active with WOCBP on the use of highly effective methods of contraception. Highly effective methods of contraception have a failure rate of < 1% when used consistently and correctly.

At a minimum, WOCBP and male subjects who are sexually active with WOCBP must agree to the use of one of the highly effective methods of contraception.

HIGHLY EFFECTIVE METHODS OF CONTRACEPTION

Highly effective methods of contraception have a failure rate of < 1% when used consistently and correctly. WOCBP and female partners of male subjects, who are WOCBP, are expected to use one of the highly effective methods of contraception listed below. Male subjects must inform their female partners who are WOCBP of the contraceptive requirements of the protocol and are expected to adhere to using contraception with their partner. Contraception methods are as follows:

- 1) Progestogen only hormonal contraception associated with inhibition of ovulation
- 2) Hormonal methods of contraception including oral contraceptive pills containing combined estrogen + progesterone, vaginal ring, injectables, implants, transdermal, and intrauterine hormone releasing systems (IUS).
- 3) Nonhormonal IUDs, such as ParaGard
- 4) Bilateral tubal occlusion
- 5) Vasectomized partner with documented azoospermia 90 days after procedure
 - a) Vasectomized partner is a highly effective birth control method provided that partner is the sole sexual partner of the WOCBP trial participant and that the vasectomized partner has received medical assessment of the surgical success.
- 6) Intrauterine hormone-releasing system (IUS)
- 7) Complete abstinence
 - a) Complete abstinence is defined as the complete avoidance of heterosexual intercourse
 - b) Complete abstinence is an acceptable form of contraception for all study drugs and must be used throughout the duration of the study treatment (plus 5 half-lives of the investigational drug plus 30 days).
 - c) It is not necessary to use any other method of contraception when complete abstinence is elected.
 - d) Subjects who choose complete abstinence must continue to have pregnancy tests.
 - e) Acceptable alternate methods of highly effective contraception must be discussed in the event that the subject chooses to forego complete abstinence.
 - f) The reliability of sexual abstinence needs to be evaluated in relation to the duration of the clinical trial and the preferred and usual lifestyle of the subject.

UNACCEPTABLE METHODS OF CONTRACEPTION

- 1) Vaginal sponge with spermicides
- 2) Progestin-only pills

- 3) Cervical cap with spermicides
- 4) Diaphragm with spermicides
- 5) Periodic abstinence (calendar, symptothermal, post-ovulation methods)
- 6) Withdrawal (coitus interruptus)
- 7) Spermicide only
- 8) Lactation amenorrhea method (LAM)
- 9) Male condoms with or without spermicide for partners of female subjects, as the only method of contraception
- 10) Female condoms
- 11) A male and a female condom must not be used together

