5 STUDY ASSESSMENTS AND PROCEDURES

5.1 Flow Chart/Time and Events Schedule

Table 5.1-1: Screening Procedure Outline (CA209171)

Procedure	Screening Visit ^a	Notes
Eligibility Assessments		
Informed Consent	X	
Inclusion/Exclusion Criteria	X	Assessed prior to first dose
Medical History	X	Medical history will include smoking history, comorbidities, particularly chronic pulmonary and chronic cardiovascular diseases following international established categories (eg, NYHA for cardiac insufficiency). Mutation status of EGFR and ALK will be collected and ROS, MET, KRAS, and BRAF will be collected, if available. Additional biopsies for mutation status, if not previously tested, are not required.
Safety Assessments		
HIV testing (in Germany only)	X	
Physical Examination	X	Includes height, weight, and ECOG PS. Focused physical exam may be performed at screening if clinically indicated.
ECOG Performance Status	X	Subgroup 1: PS 0-1 Subgroup 2: PS 2
Vital Signs and Oxygen Saturation	X	Temperature, BP, HR, RR, O2 saturation by pulse oximetry at rest (also monitor amount of supplement oxygen if applicable). Obtain vital signs at screening visit and within 72 hours of first dose.
Assessment of Signs and Symptoms	X	After obtaining Informed Consent, assess all signs and symptoms within 14 days of first dose, prior to study treatment initiation.
██████████	█	██████████
Serious Adverse Events Assessment	X	
Adverse Events Assessment	X	

Table 5.1-1: Screening Procedure Outline (CA209171)

Procedure	Screening Visit ^a	Notes
[REDACTED]	■	[REDACTED]
Pregnancy Test	X	Performed within 24 hours prior to first dose for WOCBP only (serum or urine as required by the standard of care at the site)
Additional Assessments		
[REDACTED]	■	[REDACTED]
Efficacy Assessment		
Screening/Baseline Tumor Assessment		Chest, abdomen, pelvis, brain, and all other known sites of disease within 28 days prior to first dose of study therapy. Subjects must have evaluable disease by CT or MRI per RECIST 1.1 criteria (radiographic tumor assessment performed within 28 days of first dose of study drug) or clinically apparent disease that the investigator can follow for response.

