5.3.3 Pregnancy Testing

Pregnancy testing must be completed for WOCBP at screening, within 24 hours prior to start of study drug (an extension up to 72 hours prior to start of study drug may be permissible in situations where results cannot be obtained within a 24 hour window), every 4 weeks while receiving the program drugs, and every 4 weeks for 6 months following the end of treatment. Pregnancy testing can be completed more frequently if required by local standards. Pregnancy testing may be performed at home if an in-office visit is otherwise not required. Telephone contacts are required to obtain results for all subjects who perform post-treatment at-home pregnancy testing. Although testing may be performed with home pregnancy testing kits, any positive result must be confirmed by serum pregnancy testing at the program site.

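### The protocol's reproductive rules are inconsistent on the pregnancy-test window, progestogen-only pills and the duration of abstinence, and the passages need reconciling

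*Protocol*

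**What the plan says.** **Pregnancy-test window.** For women of childbearing potential (WOCBP), inclusion criterion 3b in Protocol 3.3.1 requires a negative serum or urine test: "minimum sensitivity 25 IU/L or equivalent units of HCG) within 24 hours prior to the start of study drug". The screening schedule, Table 5.1-1, says the same: "Performed within 24 hours prior to first dose for WOCBP only". Neither gives an exception or refers to another section. Section 5.3.3 repeats the 24-hour rule and then qualifies it: "an extension up to 72 hours prior to start of study drug may be permissible in situations where results cannot be obtained" inside 24 hours.

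**Progestogen-only contraception.** Item 1 of the highly effective methods in 3.3.1 is "Progestogen only hormonal contraception associated with inhibition of ovulation", with no limit by route. Item 2 of the unacceptable methods in the same section is "Progestin-only pills", with no qualifier.

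**Duration.** Criterion 3d asks WOCBP to use contraception for treatment plus about 5 half-lives plus 30 days, given as 5 months. Criterion 3e asks men who are sexually active with WOCBP for treatment plus about 5 half-lives "plus 90 days (duration of sperm turnover) for a total of 7 months post-treatment completion". Complete abstinence is item 7 on the highly effective list, which is addressed to both groups. Item 7b says that it "must be used throughout the duration of the study treatment (plus 5 half-lives of the investigational drug plus 30 days", and does not distinguish men from women.

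**How strictly the criteria bind.** Section 3.3 makes the criteria mandatory for entry, and the close of 3.3.2 insists that each be met in full. Section 9.1.1 bars unapproved departures from the protocol except to remove an immediate hazard.

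**The concern.** These passages govern possible fetal exposure to study drug. Pregnancies are reported under the SAE procedures (Sections 6.1.1 and 6.4).

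A site that relies on the 5.3.3 extension cannot tell from the protocol whether it has followed an allowed exception or enrolled a subject who fails an inclusion criterion. A site checking a woman's contraceptive method could accept or refuse the same product, depending on which list it reads. A man who elects abstinence has two stated end dates for the precaution. In each case the protection a subject receives may depend on the page the site consults, not on a decision by the sponsor.

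**Working it through.** This is mainly a comparison of texts. The only arithmetic concerns the window and the durations.

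**1. Test window**

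| Source | Window | Exception |
|---|---|---|
| 3.3.1, criterion 3b | 24 h | none stated |
| Table 5.1-1 | 24 h | none stated |
| 5.3.3 | 24 h | up to 72 h may be allowed if results cannot be obtained within 24 h |

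The band in dispute is 72 − 24 = 48 hours wide. Take a WOCBP tested 48 hours before first dose because a result could not be obtained within 24 hours. Section 5.3.3 allows that she may be dosed. Under 3b and Table 5.1-1 her test is out of window, and 3.3.2 leaves no room for a criterion that is only partly met. The two outcomes differ for the same subject on the same facts. Outside the stated condition there is no conflict, because all three places then require 24 hours.

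**2. Progestogen-only products**

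The acceptable entry has one condition, inhibition of ovulation, and no restriction by route. The unacceptable entry has one condition, that the product is a progestin-only pill, and no reference to its mechanism. A progestogen-only pill that inhibits ovulation would satisfy both. The documents do not say whether any such product exists, so the overlap is one of wording.

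**3. Durations**

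Inputs: 5 months (3d), 7 months (3e), and the SAP Section 8 convention of 1 month = 30.4375 days. First, check that the protocol's own totals agree with each other by backing out 5 half-lives from each:

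- From 3d: 5 × 30.4375 − 30 = 152.19 − 30 = 122.2 days.
- From 3e: 7 × 30.4375 − 90 = 213.06 − 90 = 123.1 days.

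The two differ by 0.9 day, so the 5- and 7-month totals are consistent.

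Next, set item 7b against them:

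- 7b with the value from 3d: (122.19 + 30) / 30.4375 = 5.00 months.
- 7b with the value from 3e: (123.06 + 30) / 30.4375 = 5.03 months.
- Gap between 7b and 3e: 90 − 30 = 60 days, and 60 / 30.4375 = 1.97 months.

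Item 7b therefore carries the duration that 3d sets for women, with nothing to say that it applies to women only.

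**The case against.** A reader might infer that on all three points the same subject is both eligible and ineligible. The documents do not support that.

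- **Abstinence.** This is where the inference fails outright. How long a precaution lasts after treatment cannot decide who enters. Criterion 3e covers only men who are sexually active with WOCBP, so a man who is abstinent is arguably outside it, and if he resumes within 7 months he is back under it. Item 7e also requires other highly effective methods to be discussed with anyone giving up abstinence. To say that he is released 60 days early therefore goes too far. Item 7 also reads as written for women: 7d requires continued pregnancy tests, and 30 days is the ovulatory-cycle term in 3d. What stands is that 7b does not state sex, that the list is addressed to men as well, and that the glossary (Section 10) singles out female subjects for testing within a definition of abstinence not otherwise limited by sex.
- **Test window.** It is tempting to set 24 against 72 hours as two rival rules. Section 5.3.3 in fact starts from the same 24 hours and adds a conditional, discretionary exception. Exclusion 5b separately bars women with a positive test at enrollment or before study medication, whichever window is used. What stands is that the exception appears in neither 3b nor Table 5.1-1, while the criteria must be met in full.
- **Progestogen-only products.** The two entries can be read together: the specific bar on pills governs, and other progestogen-only ovulation inhibitors remain acceptable. Item 2 of the highly effective list supports this, since the only pills it names are combined ones. Against it, items 2 and 6 already cover injectables, implants and hormone-releasing intrauterine systems, so an item 1 that excludes pills adds little. The literal overlap remains, but it is open to a harmonising reading.
- **Deviations.** A reader might infer that eligibility deviations can no longer be classified. The programmable entry deviations in SAP 7.2.2 concern histology, measurable disease and prior therapy. None is reproductive. Other eligibility deviations go to data management listings, so any ambiguity is confined to those.

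**Conclusion.** The reproductive rules are internally inconsistent, to different degrees:

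1. The test window is a real conflict at entry. It is limited to WOCBP tested more than 24 and up to 72 hours before first dose under the 5.3.3 condition.
2. The progestogen-only overlap exists on a literal reading only.
3. The abstinence term is a 60-day mismatch (about 5 against 7 months) in how long a precaution lasts. It does not affect eligibility.

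The documents give neither the number of WOCBP nor the number of men with WOCBP partners. That few of the roughly 800 treated subjects are affected is an assumption. No endpoint, sample size or analysis changes. The case for acting rests on subject safety and on sites being able to apply one stated rule.

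**What to change.** In the next amendment, with matching consent text:

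- Make criterion 3b, Table 5.1-1 and Section 5.3.3 state the same pregnancy-test window and the same exception, if there is to be one, with its condition.
- Word the two contraception lists so that no progestogen-only product can fall on both.
- Have item 7b refer to the durations in 3d and 3e by sex, instead of giving one figure for all subjects.

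Which window, product list or duration is right is for the sponsor to decide, and none is proposed here. The cost is wording in the protocol and consent form. No new procedures are needed, and the SAP's analyses are untouched.

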3.3.2 Exclusion Criteria

1) Target Disease Exceptions

- a) Subjects with untreated, symptomatic CNS metastases are excluded.
- b) Subjects with carcinomatous meningitis are excluded.

2) Medical History and Concurrent Diseases

- a) Subjects with active, known or suspected autoimmune disease. Subjects with Type I diabetes mellitus, residual hypothyroidism due to an autoimmune condition requiring hormone replacement, psoriasis not requiring systemic treatment, or conditions not expected to recur in the absence of an external trigger are permitted to enroll.
- b) Subjects with a condition requiring systemic treatment with either corticosteroids (> 10 mg daily prednisone equivalent) or other immunosuppressive medications within 14 days of the first dose of study drug administration. Inhaled or topical steroids and adrenal replacement steroid doses > 10 mg daily prednisone or equivalent are permitted in the absence of active autoimmune disease
- c) As of Amendment 01, this criterion is no longer applicable.
- d) Other active malignancy requiring concurrent intervention
- e) Subjects with previous malignancies (except non-melanoma skin cancers, and the following in situ cancers: bladder, gastric, colon, endometrial, cervical/dysplasia, melanoma or breast) are excluded unless a complete remission was achieved at least 2 years prior to study entry AND no additional therapy is required during the study period
- f) Any serious or uncontrolled medical disorder or active infection that, in the opinion of the investigator, may increase the risk associated with study participation, study drug administration, or would impair the ability of the subject to receive protocol therapy
- g) All toxicities attributed to prior anti-cancer therapy other than alopecia and fatigue must have resolved to Grade 1 (NCI CTCAE version 4) or baseline before administration of study drug.
- h) Subjects must have recovered from the effects of major surgery or significant traumatic injury at least 14 days before the first dose of study treatment.
- i) Known alcohol or drug abuse

- j) Subjects who received prior therapy with anti-PD-1, anti-PD-L1, anti-PD-L2, anti-CD137, or anti-CTLA-4 antibody (including ipilimumab or any other antibody or drug specifically targeting T-cell costimulation or checkpoint pathways) or who have previously taken part in a randomized BMS clinical trial for nivolumab or ipilimumab.

3) Physical and Laboratory Test Findings

- a) Known history of testing positive for human immunodeficiency virus (HIV) or known acquired immunodeficiency syndrome (AIDS).
- b) Any positive test for hepatitis B virus or hepatitis C virus indicating acute or chronic infection.

4) Allergies and Adverse Drug Reactions

- a) History of severe hypersensitivity reactions to other monoclonal antibodies
- b) As of Amendment 01, this criterion is not applicable.

5) Sex and Reproductive Status

- a) WOCBP who are pregnant or breastfeeding
- b) Women with a positive pregnancy test at enrollment or prior to administration of study medication

6) As of Amendment 01, this section was removed.

- a) As of Amendment 01, this criterion was removed.
- b) As of Amendment 01, this criterion was removed.
- c) As of Amendment 01, this criterion was removed.
- d) As of Amendment 01, this criterion was removed.
- e) As of Amendment 01, this criterion was removed.

7) Other Exclusion Criteria

- a) Prisoners or subjects who are involuntarily incarcerated
- b) Subjects who are compulsorily detained for treatment of either a psychiatric or physical (eg, infectious disease) illness

Eligibility criteria for this study have been carefully considered to ensure the safety of the study subjects and that the results of the study can be used. It is imperative that subjects fully meet all eligibility criteria.

